#### 16.6 Economic evaluation

An economic analysis will be conducted alongside both trials. The following common methods will be used in both studies. Costs will be based on an NHS perspective and a standard price year, and include details of all AED treatment and hospital admissions (we propose to extract the latter from the NHS Digital Hospital Episode Statistics (HES) database). Resources associated with AED treatment will thereby be monitored along with original length of stay and any hospital re-admissions.

In terms of outcomes, data on quality of life, measured using the EQ-5D-5L , will be requested at neuroscience unit (NSU) discharge, 6, 12, 18 and 24 months post-enrolment (if

the participant cannot complete the EQ-5D-5L themselves, we will request that a relative/friend complete the proxy version). This will enable Quality Adjusted Life Year (QALY) scores to be estimated using the total area under the curve method , taking account of the latest appropriate guidance .

The within trial analysis will be conducted on an intention to treat basis over a 24-month period, with appropriate discounting . Assuming the level of missing data is not large i.e. <20% a complete case analysis will be undertaken. Alternatively, multiple imputation will be undertaken, where patterns of missing data would be examined to infer the assumed missing data mechanism . Regression analysis will be used to estimate the incremental cost and incremental effect (QALY gain) associated with both a longer course of AED (phenytoin or levetiracetam) compared to a shorter course of AED (MAST-DURATION) and a 7-day course of AED (phenytoin or levetiracetam) compared to no AED (MAST-PROPHYLAXIS).

Assuming dominance does not occur (this would be apparent if one intervention was both more costly and less effective), the incremental cost-effectiveness ratio (ICER) will be estimated (mean incremental cost/mean incremental effect) by comparing the remaining interventions in both studies. These ICERs will then be compared to thresholds of cost-effectiveness  in order to consider the potential value for money/make recommendations about provision in the NHS. Additionally, the associated level of uncertainty will also be estimated, where the cost-effectiveness acceptability curve (CEAC) will be calculated. The CEAC estimates the probability of the intervention being cost-effective at various levels of willingness to pay .

Finally, sensitivity analysis  will be undertaken on the above base-case analysis to assess whether the associated conclusions are robust to changes in key assumptions. Potential sensitivity analysis would include an assessment of whether results are robust to different assumptions about missing data and could be based on a complete case approach if MI were used in the base-case, or MI could be undertaken if a complete case approach was undertaken in the base-case. Another sensitivity analysis might be to adopt as per protocol approach and exclude any individuals who did not receive the treatment to which they were assigned.

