#### 16.5 **Procedure to account for missing or spurious data**

For the primary analysis missing data will be assumed to be missing at random. A sensitivity analysis will be carried out by performing a complete case analysis. As the relevant covariates need to be recorded before the patient can be randomised, we aim to have minimal missing baseline data. There is also an excellent track record for UK-led neurosurgical studies in achieving extremely high rates for follow-up (STICH, STICH II and RESCUEicp studies).

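### The cost-effectiveness base case is complete-case whenever missing data are under 20%, a threshold with no unit, in an analysis described as intention to treat

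*Protocol*

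**What the plan says.** Protocol section 16.6 (Economic evaluation) fixes four things that bear on each other.

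- **Principle:** "The within trial analysis will be conducted on an intention to treat basis over a 24-month period".
- **Outcome:** the EQ-5D-5L "will be requested at neuroscience unit (NSU) discharge, 6, 12, 18 and 24 months post-enrolment", and "This will enable Quality Adjusted Life Year (QALY) scores to be estimated using the total area under the curve method". That is five measurement points. If a participant cannot answer, "we will request that a relative/friend complete the proxy version".
- **Missing data:** "Assuming the level of missing data is not large i.e. <20% a complete case analysis will be undertaken". For the other branch: "Alternatively, multiple imputation will be undertaken, where patterns of missing data would be examined to infer the assumed missing data mechanism".
- **Sensitivity analysis:** among the possible checks, "MI could be undertaken if a complete case approach was undertaken in the base-case".

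Section 16.6 does not say whether the 20% is a share of forms, of values or of participants. It does not say whether a gap between two observed points may be interpolated, or how a death enters the QALY.

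Elsewhere, section 16.1 defines the intention-to-treat set as everyone randomised. Section 16.3 assumes 12% drop-out in both trials. For the clinical primary analysis, section 16.5 assumes data missing at random and adds: "A sensitivity analysis will be carried out by performing a complete case analysis".

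**The concern.** A QALY built from five repeated questionnaires is complete only for people who supply what the area calculation needs over 24 months. A complete-case base case restricts the incremental QALY to those people and sets aside the EQ-5D-5L answers already given by everyone else. That set is not everyone randomised, so the result would not be the intention-to-treat estimate that the section promises. After traumatic brain injury, returning a questionnaire plausibly depends on recovery, so full responders may not represent their arm. The protocol's ICERs and acceptability curves are meant to inform NHS provision, so the choice of base case matters.

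The rule is also ambiguous. Because the 20% has no unit, the same data can fall on either side of it, depending on how the share is counted.

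**Working it through.** **Inputs from the protocol:** five EQ-5D-5L points (16.6); totals of 1221 and 428, with 358 and 188 observations per arm (16.3); 12% drop-out (16.3); the 20% threshold (16.6). The PROPHYLAXIS table in section 11.6, as extracted, shows the first EQ-5D-5L at Day 14, whereas 11.5.2 and 16.6 place it at discharge. The count is five either way. **Assumed, because the protocol gives no such figure:** the missing rate per form and how misses overlap between forms.

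**1. The plan's own totals.** Observed total divided by (1 − drop-out):

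- MAST-PROPHYLAXIS: 3 × 358 / 0.88 = 1220.5, rounded up to 1221.
- MAST-DURATION: 2 × 188 / 0.88 = 427.3, rounded up to 428.

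Both reproduce. They serve here only as denominators; the 20% is a chosen rule with no derivation to reproduce.

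**2. Which branch the plan's own assumption points to.** 12% is below 20%, so if drop-out is the main source of missing data, the complete-case branch applies. If each drop-out lacks at least the last form:

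- 0.12 × 1221 = 146.5, about 147 participants.
- 0.12 × 428 = 51.4, about 51 participants.

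Someone who leaves after 12 months has usually given the discharge, 6-month and 12-month values, and these would not be used.

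**3. If the 20% counts incomplete participants.** The loss is capped below 0.20 × 1221 = 244.2 and 0.20 × 428 = 85.6. With independent misses, staying under the cap needs a missing rate per form below 1 − 0.8^(1/5) = 4.4%.

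**4. If the 20% counts forms.** Let m be the missing rate per form, with no interpolation. The complete share is 1 − m if the same people miss every form and (1 − m)^5 if misses are independent.

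| m (assumed) | Complete, full overlap | Complete, independent |
|---|---|---|
| 5% | 95% (1160; 407) | 77% (945; 331) |
| 10% | 90% (1099; 385) | 59% (721; 253) |
| 19% | 81% (989; 347) | 35% (426; 149) |

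Counts are participants out of 1221 and out of 428. At m = 10% the loss is therefore 10% to 41%.

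**5. Why the unit matters.** Take m = 10% with independent misses. Counted by form, missingness is 10%, under the threshold, so the base case is complete case and loses 41%. Counted by participant, 41% are incomplete, over the threshold, so the base case is multiple imputation. The text does not say which applies.

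**The case against.** The strongest defence is that the rule is pre-specified. Both branches are named in advance, and the switch depends on how much is missing, not on the treatment effect. If the threshold counts participants, which is at least as natural for a complete-case rule, the loss is under 20% and every independent-miss scenario tabulated would trigger imputation. Proxy completion (16.6) and telephone contact after an unreturned questionnaire (11.7) will reduce gaps. Imputation is named as a possible check on a complete-case base case. The analysis is secondary and touches neither primary outcome.

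Much of this stands, and it rules out several stronger readings that a reader might infer:

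- **That deaths, including deaths before discharge, drop out.** The protocol does not say so. Section 14.1.1 records all-cause mortality to 24 months, a known death can be scored and is then not missing, and such scoring is commonly left to an analysis plan.
- **That 16.6 contradicts 16.5.** Section 16.5 governs the clinical primary analysis; 16.6 sets its own rule for a different one. The different order is worth noting but is not an inconsistency.
- **That imputation is used only at 20% or more.** It may also be run as a sensitivity analysis.
- **That one missed form always removes a participant, or that cost data are discarded with it.** The text settles neither interpolation nor the handling of costs, and admissions are proposed from routine hospital data.

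The defence does not supply a unit for the 20%. It does not reconcile complete case with including everyone randomised. It also does not turn an optional imputation check into a commitment.

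**Conclusion.** The point holds in a limited form. Section 16.6 makes complete case the base case below an undefined 20%, inside an analysis it calls intention to treat, with imputation then only optional. The plan's 12% drop-out points to that branch, and about 147 of 1221 and 51 of 428 participants could leave the base case with their earlier EQ-5D-5L answers unused. These counts assume that the 12% carries over to the 24-month questionnaires and that none of those people is a death scored in the QALY.

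Beyond that there is only a range: under 20% lost if the threshold is per participant, and 10% to 41% lost at an assumed 10% missing per form if it is per form. The larger losses in the table need a per-form reading, independent misses and no interpolation all at once, so they are not a forecast. The size and direction of any bias in the incremental QALY cannot be computed, because the protocol gives no EQ-5D-5L completion or mortality rates. The change is worth making because the better method is already in the plan as its alternative.

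**What to change.** In section 16.6:

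1. Make multiple imputation by arm, under missing at random, the base case at any level of missingness.
2. Delete the 20% switch. This also removes the need to define its unit.
3. Keep complete case as a sensitivity analysis, worded as a commitment and not as a possibility.
4. For clarity, state that known deaths take utility 0 from the date of death and so are not counted as missing.

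The cost is a wording change and slightly more analysis work. No data collection, sample size or primary analysis changes.

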## 8 Trial Design

## 8.1 Statement of Design

MAST-PROPHYLAXIS: A multi-centre, pragmatic, three arm, open label, randomised trial aiming to determine the comparative clinical and cost-effectiveness of a 7-day course of phenytoin or levetiracetam, used as seizure prophylaxis, versus no AED for TBI patients.

MAST-DURATION: A multi-centre, pragmatic, two arm, parallel, open label, randomised trial aiming to determine the comparative clinical and cost-effectiveness of a longer course of phenytoin or levetiracetam (at least 6 months post-TBI) versus a shorter course (up to 3 months) for TBI patients with early seizures (within first 7 days following trauma).

Both studies will be preceded by an internal pilot in order to confirm recruitment, randomisation, treatment, and follow-up assessments. We have defined robust progression criteria, on the basis of recently published recommendations . On reaching, the pre-defined success criteria, the internal pilot studies will run seamlessly into the main trials.

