# 9.3 Treatment Assignment

## MAST-PROPHYLAXIS

Patients who fulfil the eligibility criteria will be randomly assigned to either phenytoin, levetiracetam or no AED for a period of 7 days. The distribution between trial populations will be 1:1:1 (phenytoin : levetiracetam : no AED).

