## 16 Statistics

### 16.1 Statistical methods

The main statistical analysis will be performed on an intention-to-treat basis, which will include all randomly assigned participants.

The primary endpoint (occurrence of PTS) is binary (yes / no). The primary analysis will estimate the absolute difference between the active treatment groups and control in terms of the incidence of PTS using logistic regression with an additive link, adjusting for baseline covariates (subdural haematoma (yes / no), number of lobes with a contusion (none / one / two / more than two), craniotomy or craniectomy (yes / no), depressed skull fracture (yes / no), initial severity of injury GCS 3-8 / 9-15, intradural lesion (yes / no) and will furnish the estimates with 95% confidence intervals. MAST DURATION will use a standard 2-sided p-value compared to a 5% significance level; MAST-PROPHYLAXIS will adjust for multiple testing using Dunnett's test at an overall 5% significance level stipulating that the smaller of the 2-sided p-values must be less than 2.7% to achieve statistical significance. A direct comparison between active arms (phenytoin vs levetiracetam) in MAST-PROPHYLAXIS will be a secondary analysis. The baseline covariates will be those used to stratify the randomisation: depressed skull fracture (yes / no), intradural lesion (yes / no) and initial severity of injury (GCS 3-8, GCS 9-15). Site will be handled as a random effect as there are anticipated to be 29 sites.

Sensitivity analyses will be performed to assess the influence of missing data and deviations from the intention-to-treat principle.

The GOSE will be analysed with an ordinal method adjusting for baseline covariates. Further secondary endpoints will be summarized using appropriate techniques according to whether the variable is binary, categorical, continuous or time-to-event. Categorical and binary variables will be summarized using bar charts, frequency tables and comparisons made using logistic regression.

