### MAST-PROPHYLAXIS

According to the available evidence (5,6), a treatment effect of 7% can be expected with seizure prophylaxis. We will attempt to reproduce these findings in a multi-centre setting across the NHS. Recruiting 1221 patients overall will provide 358 observations per arm. Assuming seizure rates of 4% in both active arms and 11% in control will provide 90% power to achieve significance in both comparisons. Alternatively, if only one active arm has a seizure rate of 4% and the other the same rate as control, then there will be 91% power to achieve significance in that individual comparison. The expected average annual recruitment is 15-20 patients / site. We will aim to roll out the trial in 29 adult trauma-receiving hospitals in the UK. According to the timeline presented below, the recruitment will be completed in 3 years.

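### The PROPHYLAXIS economic contrast in section 16.6 reads as one AED-versus-none comparison, which does not fit the three-arm, per-drug design and should be reconciled

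*Protocol*

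**What the plan says.** Section 16.6 introduces methods common to both trials. One sentence then gives the regression contrasts as a pair: longer versus shorter treatment for MAST-DURATION, and "a 7-day course of AED (phenytoin or levetiracetam) compared to no AED (MAST-PROPHYLAXIS" for MAST-PROPHYLAXIS. The same parenthesis naming the two drugs appears in each half. The next paragraph deals with dominance and says ICERs will be estimated "by comparing the remaining interventions in both studies". It continues: "These ICERs will then be compared to thresholds of cost-effectiveness", with a view to recommendations on NHS provision. The acceptability curve is described for a single intervention.

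Elsewhere the trial is set up drug by drug:

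- Section 9.3: "The distribution between trial populations will be 1:1:1 (phenytoin : levetiracetam : no AED".
- Section 16.1: the primary analysis estimates the "absolute difference between the active treatment groups and control in terms of the incidence of PTS", with Dunnett's adjustment and a 2.7% threshold for the smaller p-value. It adds: "A direct comparison between active arms (phenytoin vs levetiracetam) in MAST-PROPHYLAXIS will be a secondary analysis".
- Section 16.3: power is also given for the case "if only one active arm has a seizure rate of 4% and the other the same rate as control".

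Section 8.1 states the aim as the "comparative clinical and cost-effectiveness of a 7-day course of phenytoin or levetiracetam, used as seizure prophylaxis, versus no AED".

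**The concern.** In MAST-DURATION the randomised factor is duration and the drug is a local choice, so a contrast that pools the drugs is the right one. In MAST-PROPHYLAXIS the drug is the randomised factor. The same form of words there, read literally, gives one active group made of two arms.

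A pooled ICER would describe a mixture of two drugs, whereas a provision decision has to be made for each. If the drugs differ in effect, tolerability or cost, the mixture can make a poor drug look acceptable or hide a good one. Cost-effectiveness is part of the stated aim in 8.1, and the ICERs are meant to inform NHS provision, so the choice of contrast matters. An analyst working from the regression sentence and one working from the dominance paragraph could reach different deciding results.

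**Working it through.** **1. Is the clinical design per drug?** The inputs are all from sections 16.1 and 16.3: 358 observations per arm, 12% drop-out, 4% versus 11%, Dunnett at 5% overall.

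- Total: 3 × 358 = 1074, and 1074 / 0.88 = 1220.5, rounded up to 1221. This matches.
- Dunnett, two comparisons sharing a control (correlation 0.5): two-sided critical value 2.212, p = 0.02696. This matches the stated 2.7%.
- Power for one drug against control, with mean rate 0.075:
  - standard error under the null = √(2 × 0.075 × 0.925 / 358) = 0.01969
  - standard error under the alternative = √((0.11 × 0.89 + 0.04 × 0.96) / 358) = 0.01951
  - z = (0.07 − 2.212 × 0.01969) / 0.01951 = 1.356, so power is 91.2%. The protocol states 91%.

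The stated figures reproduce, and they belong to separate drug-versus-control comparisons.

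**2. Which contrast does 16.6 fix?**

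| Text | Points towards |
|---|---|
| 16.6 regression sentence: a pair of contrasts, one per trial, same drug parenthesis in each | one pooled contrast |
| 16.6 acceptability curve: one intervention, singular | one pooled contrast |
| 16.6 dominance step: several ICERs among those remaining | three strategies |
| 9.3, 16.1, 16.3: three arms, per-drug tests, one-drug scenario | three strategies |

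The dominance step does not settle the matter. It is written for both studies, including two-arm MAST-DURATION.

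**3. Effect of pooling on seizures, protocol figures only.** In the scenario with one drug at 4%, the other at 11% and control at 11%:

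- per drug: 11 − 4 = 7 points and 11 − 11 = 0 points
- pooled: 11 − (4 + 11) / 2 = 3.5 points

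**4. Effect of pooling on net benefit.** For drug j, net benefit is NB_j = λ × ΔQALY_j − Δcost_j. With equal arms, NB_pooled = (NB_A + NB_B) / 2.

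The protocol gives no threshold value, cost or QALY gain, so every input below is assumed. Drug B is given zero QALY effect and the same added cost as drug A.

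| λ (£/QALY) | Gain, drug A | Added cost, each drug | NB, A | NB, B | NB, pooled |
|---|---|---|---|---|---|
| 20,000 | 0.02 | £100 | +300 | −100 | +100 |
| 20,000 | 0.01 | £150 | +50 | −150 | −50 |
| 30,000 | 0.02 | £100 | +500 | −100 | +200 |
| 30,000 | 0.01 | £150 | +150 | −150 | 0 |

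In rows 1 and 3 drug B is carried in with drug A. In row 2 drug A is rejected with drug B. In row 4 the pooled result is a tie.

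Under these assumptions, write q for A's gain and c for the added cost. Drug A is worthwhile when c < λq, while the pooled value is λq/2 − c. For any 0 < c < λq, apart from the tie at c = λq/2, the pooled sign is wrong for exactly one of the two drugs.

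**5. Cost in precision of separating the drugs.** With equal arms of size n and equal variance σ², the contrast variance is σ²(1/n + 1/n) = 2σ²/n per drug and σ²(1/n + 1/(2n)) = 1.5σ²/n pooled. The ratio of standard errors is √(2 / 1.5) = 1.155, so a per-drug interval is about 15% wider.

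**The case against.** The strongest reply is that no pooling is planned and the sentence is only compressed.

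- Sections 8.1 and 8.5.1 use the same either-drug wording for the aim and the primary objective, and 16.1 carries the clinical objective out as two comparisons. The economic sentence may be the same shorthand.
- The dominance step makes most sense with three options. In a two-option comparison, removing one leaves nothing to compare.
- EQ-5D-5L, from which QALYs are built, is listed in 8.5.1 among outcomes compared across three arms.
- Model coding and curve layout commonly belong in an analysis plan, which is not shown here.
- Readers would also have the per-drug clinical results beside any pooled ICER.

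Much of this stands. A reader might infer that the protocol has decided to pool the arms and will therefore misjudge a drug. The text does not support that: pooling is nowhere stated, and part of 16.6 points the other way. A reader might also infer that the pooled QALY gain must be half that of the working drug. That assumes the other drug has exactly zero QALY effect, and the protocol gives no link between two-week seizures and 24-month QALYs.

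The reply does not remove the inconsistency. The clinical section has a sentence that turns the shorthand into separate comparisons, and the economic section has none. No per-drug cost or QALY contrast, and no economic drug-versus-drug comparison, is written. Which interventions are compared is the economic question itself, and the protocol has already put an answer in words.

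**Conclusion.** The point holds as a conflict of wording within 16.6, and between 16.6 and sections 9.3, 16.1 and 16.3. It is a cheap improvement and not a demonstrated error of analysis.

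The size that rests on protocol figures alone is the dilution of the seizure difference to 3.5 points, in a scenario the protocol itself considers. It arises only if the arms are pooled. The averaging of net benefit is an identity for equal arms. Whether its sign misleads depends on real differences between the drugs and on costs, gains and a threshold that the protocol does not state. The pound figures show that a reversal is possible and do not estimate how likely it is. The primary analysis and the sample size of 1221 are unaffected.

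**What to change.** In 16.6, state that for MAST-PROPHYLAXIS phenytoin, levetiracetam and no AED are three separate strategies. Estimate mean costs and QALYs per arm, for example with arm as a three-level factor in the planned regression. Then carry out a full incremental analysis: order the strategies, remove dominated options and report ICERs among those remaining, including drug against drug where both remain. Extend the acceptability curve to all three options. Keep the contrast that pools the drugs for MAST-DURATION only.

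This is a change of wording, using the same data and the same type of model, with no extra patients. The downside is the wider interval for each drug shown above. It is best settled before unblinded data are seen, so that the contrast cannot be chosen in light of the results.
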